11.5 Follow-up diagnostics

Protocol specific follow-up MR diagnostic scan is required for patient visit at one and six months after end of radiotherapy or at progression of the dominant symptom. The MR diagnostics should be performed according to the specifications in appendix 2. Remission status evaluated at 6 month based on available clinical data. Follow-up MR Scans will be co-registered to the baseline MR scan. Comparative volume and ADC statistics will be calculated as surrogate markers of response to radiotherapy.

12 Safety management

12.1 Adverse events

An adverse event (AE) is defined as any event experienced by a patient or subject of a clinical trial, which does not necessarily have a causal relationship to the study treatment.

The severity of AEs should be assessed by using the National Cancer Institute Common Terminology Criteria for Adverse Events (CTCAE version 4.03). If an AE occurs, which is not described in the CTCAE version 4.03, the following five-point scale should be used for assessment: grade 1 = mild, grade 2 = moderate, grade 3 = severe, grade 4 = life-threatening and grade 5 = fatal.

The investigator must also systematically assess the causal relationship of the AEs to the trial treatment. The AEs should therefore be classified as reasonably related or not reasonably related (unrelated) to trial treatment.

- All AEs experienced will be documented in the appropriate section of the CRF.
- Any clinical AE with severity of grade 4 or 5 must also be reported as an SAE.

Severe adverse events (SAE)

A severe adverse event (SAE) is any untoward medical occurrence that meets the following criteria:

- Results in death.
- Is life-threatening
- Requires hospitalization or prolongs an existing hospitalization.
- Results in persistent or significant disability
- Is a congenital anomaly or birth defect.
- Is otherwise considered medically important.

All SAEs must be documented and reported to the sponsor within 24 hours after awareness of the event using the online web interface for Easytrial.

13 Data and Safety Monitoring Board

Data will be entered pseudonymously into an online web based electronic database, Easytrial, and data stored on servers in Denmark. Access to the web interface is by invitation via email to staff participating in the study only. The Data and Safety Monitoring Board (DSMB) reviews safety after the first ten and after the

last patient have been treated and the respective data validated and tabulated. It may recommend restrictions to treatment regimens and patient eligibility.

14 Endpoint Adjudication Committee

The Endpoint Adjudication Committee (EAC) receives pseudonymized MRI scans and the Radiotherapy treatment plan for all patients up to end of trial. The EAC will assess when progression free survival ended.

15 Quality Assurance

The Monitoring at the German sites according to GCP is performed by ZKS Kiel/Luebeck.

The Danish sites will be monitored according to the Danish regulations in their own responsibility.

16 Statistical aspects

16.1 Case number

The objective of this study is to investigate the feasibility of applying hypo-fractionated radiotherapy to treat a dominant symptomatic lesion in patients with HRPC. The hypothesis is that at least 90% of the recruited patients complete combined systemic and local treatment with at least 90% of scheduled radiation dose administered. We use a two-sided one-sample proportion score test to compare the proportion of feasible cases to a reference value of 90%. We want to detect any difference with statistical significance of 5% and a power of 80% for not overlooking a true proportion non-feasible of 70%. The necessary sample size is estimated to 24 cases. Drop-out may happen either due to exclusion, or because patients withdraw their consent for participation. For patients with poor prognosis a realistic drop-out rate is estimated to be 30%, which implicated that **34 patients** must be included in the study to reach significance.

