Exclusion criteria (recruitment is not possible if any -at least one- criterion is met)	
 • Relevant comorbidity (with limitations to administer radiotherapy according to protocol) • Prior radiotherapy which results in limitations to administer radiotherapy according to protocol • No large metal implants in vicinity of lesion • Department dose constraints for normal tissue can't be met • Large bony lesions with extensive osseous destruction • Patients symptoms do not correlate with MR findings
Study therapy	
 • Image guided radiotherapy (IGRT) with hypo-fractionated simultaneous integrated boost (IMRT) • GTV1 = MR T2w lesion and ADC $\leq 1200 * 10^{-3}$ mm2/s • GTV2 = MR T2w lesion and ADC \leq median ADC in GTV1 • Each lesion is a CTV, CTV = GTV • PTV=CTV+ margin according to department standards • Dose-fractionation • CTV1: 4 x 5 Gy • CTV2: 4 x 7 Gy
Primary endpoint	Feasibility: Proportion of study participants that complete radiotherapy with $\geq 90\%$ of prescribed dose
Secondary endpoints	
 • Dominant symptom (VAS) • Progression-free survival >6 months • Overall survival

	
• Acute toxicity• Quality of life• Change in ADC from before to end of treatment• Change in ADC from before to 6 month post treatment
Sample size	34 patients has to be included in the study
Study sites	University Hospital Sjaelland, Naestved UKSH Campus Kiel UKSH Campus Luebeck
Time table	Recruitment period: 12 months Start of study: March 2018 End of study: March 2019 Follow-up: minimum \geq 6 months
Financing	Interreg (InnoCan)

3 Background and rationale

Prostate cancer is the major cause of cancer death in men living in developed countries. Large autopsy studies found that patients that presented prostate cancer demonstrated metastatic disease in 35% of cases. Prostate cancer metastases were 90% bone metastases, with 90% of the bone metastases involved the spinal cord, followed by lung (46%), liver (25%) and pleura (21%). Another important pathway is the lymphatic system, which is involved in 9 to 16% of cases, especially at the level of obturator, pre-sacral, internal, and common iliac arteries, and sometimes even the extra-regional para-aortic chains (1).

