Systemic therapy will be administered according to department standard guidelines. Systemic therapy may be chemotherapy, anti-hormonal therapy, targeted therapies, bisphosphonates or a combination. The type of therapy will be documented. Interruptions of systemic therapy, delays or changes of drugs due to radiotherapy should be avoided.

10 Radiation therapy

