10.1 General remarks

The primary endpoint is feasibility. The secondary endpoints are duration of relief from local symptoms, i.e. local symptom progression free survival (LPFS), overall survival, treatment toxicity (RTOG/CTCAE 4.0), Quality of life (EORTC-QLQ-C30 and EPIC26), and change in ADC as surrogate marker of response (21-25). Patients are scheduled for protocol specific follow-up visits at 1, 3, 6 months after end of radiotherapy. Additional MRI (T2w and DWI) will be performed at 1 and 6 months after end of radiotherapy or in case of progression of the dominant symptom.

Preferred technique is hypo-fractionated with high precision radiotherapy (radiosurgery or stereotactic radiotherapy) with few (1 to 5) fractions and ablative total dose. Daily IGRT is mandatory for hypo-fractionated regimens. For the treatment of thoracic lesions and metastases in the upper abdomen, techniques for motion compensation (e.g. breath-hold- or gating techniques) should be used, if available. In specific situations (e.g. spinal metastases with involvement of the spinal canal or cord compression or metastases with infiltration of hollow organs), however, lower doses of radiotherapy may be necessary for adherence of dose constraints or to avoid radiation-induced complications such as perforation. In these cases, moderately hypo-fractionated or even conventionally fractionated regimens should be used. The total dose should exceed at least a dose equivalent to 50Gy in conventional fractionation.

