10.4 Dose specification

The dose will be prescribed as 95%-PTV-coverage. The favorite technique is ablative radiosurgery or hypo-fractionated stereotactic radiotherapy if available, otherwise VMAT or IMRT is allowed. Recommended treatment regime

Technique	Dose and fractionation regimens
Hypo-fractionated regime	PTV1: 4F x 5Gy, total dose 20Gy PTV2: 4F x 7Gy, total dose 28Gy

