16.3 Analysis

Patient and tumor characteristics are given as absolute and relative frequencies. Doses, volumes, fractions are listed by technique, by localization of metastasis, and by size. Maximum and median doses applied to organs at risk are described as median, inter-quartile range, and maximum. Summary compliance measures use the worst observation. Further parameter estimation, confidence intervals and tests using data at the metastasis level account for correlation by using GEE methods.

Toxicities are tabulated by grade and time and shown as time profiles of cumulated grades. Adverse events are listed by system organ class (MedDRA), intensity and causality. Progression free survival is estimated using the Kaplan-Meier method.

17 Early termination

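### The primary endpoint has two definitions: radiotherapy completion in the synopsis, and completion of combined systemic and local treatment in the Section 16.1 hypothesis

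*Protocol*

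**What the plan says.** The synopsis has a row labelled as the primary endpoint. It reads "Proportion of study participants that complete radiotherapy with" at least 90% of the prescribed dose, and systemic therapy does not appear in it.

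Section 16.1 opens in the same spirit: "The objective of this study is to investigate the feasibility of applying hypo-fractionated radiotherapy to treat a dominant symptomatic lesion". Its next sentence, which states the hypothesis, sets this target: "at least 90% of the recruited patients complete combined systemic and local treatment with at least 90% of scheduled radiation dose administered". The section then plans a two-sided one-sample score test of the proportion of feasible cases against 90%, without defining a feasible case any further. Sections 4 and 10.1 name feasibility as the primary endpoint and do not define it.

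On systemic therapy, Section 9 says "Systemic therapy will be administered according to department standard guidelines". It allows chemotherapy, anti-hormonal therapy, targeted therapy, bisphosphonates or a combination, asks that the type be documented, and adds: "Interruptions of systemic therapy, delays or changes of drugs due to radiotherapy should be avoided". It gives no course length, completion criterion or time window.

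On dose, Section 10.4 lists 4 x 5 Gy to PTV1 and 4 x 7 Gy to PTV2 under the label "Recommended treatment regime". Section 10.1 describes situations such as infiltration of hollow organs in which lower doses may be needed, and says "In these cases, moderately hypo-fractionated or even conventionally fractionated regimens should be used".

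**The concern.** The trial has one planned hypothesis test, and the Protocol gives two rules for scoring a patient in it. Under the synopsis a patient who receives the full radiation dose is a success whatever happens to his systemic treatment. Under the Section 16.1 hypothesis the same patient is a failure if systemic treatment is not completed. The composite can never exceed the radiotherapy-only proportion, and the two rules can lead to opposite conclusions from the same patients.

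The composite also cannot be scored as the Protocol stands, because Section 9 never says what completing systemic therapy means. Section 16.2 adds to the doubt. It has the primary endpoint reached up to 6 months after the last inclusion, yet radiotherapy should be over about 5 weeks after inclusion (3 weeks to start, Section 10.6, plus 2 weeks to deliver, Section 10.3).

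A secondary matter is what the 90% is a percentage of. The synopsis refers to the prescribed dose and Section 16.1 to the scheduled dose. If a patient is prescribed a different fractionation under Section 10.1 and completes it, he may count as feasible although he never received the regimen under study.

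**Working it through.** **1. Reproduce the plan's sample size.** Inputs from Section 16.1: reference p0 = 0.90, alternative p1 = 0.70 (read as the feasible proportion), two-sided 5%, power 80%.

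n = [(1.960 × √(0.90 × 0.10) + 0.842 × √(0.70 × 0.30)) / (0.90 − 0.70)]² = 23.7, rounded up to 24. This matches. With 30% drop-out, 24/0.70 = 34.3, stated as 34. The formula uses only p0 and p1, so n is the same under either definition.

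**2. Rejection region at n = 24.** z = (k/24 − 0.90) / √(0.90 × 0.10/24), with denominator 0.0612.

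| Successes k | z | two-sided p |
|---|---|---|
| 18 | −2.45 | 0.014 |
| 19 | −1.77 | 0.077 |
| 22 | +0.27 | 0.79 |
| 24 | +1.63 | 0.10 |

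The test rejects at 18 or fewer and never rejects upward, so the only significant result possible is a proportion below 90%.

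**3. Same patients, two answers (constructed example).** Suppose 22 of 24 complete radiotherapy. The synopsis rule gives 22/24 = 92%, p = 0.79, no rejection. Suppose four of those 22 stop systemic therapy. The Section 16.1 rule gives 18/24 = 75%, p = 0.014, and the test rejects.

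**4. The same in rates.** The Protocol gives no systemic completion rate, so the rates s below are assumptions. Radiotherapy completion is set at 90%. Under independence the composite is 0.90 × s. Without that assumption it lies between 0.90 + s − 1 and the smaller of 0.90 and s. The rejection probability is the binomial P(X ≤ 18 | 24, p).

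| Systemic completion s | Composite, independent | P(reject) | Composite, any dependence | P(reject) |
|---|---|---|---|---|
| 90% | 81% | 30% | 80–90% | 3–34% |
| 80% | 72% | 70% | 70–80% | 34–77% |
| 70% | 63% | 93% | 60–70% | 77–96% |

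Under the synopsis definition with 90% radiotherapy completion, the test rejects in 2.8% of trials.

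**5. The dose gap.** The Protocol does not say how many patients would move to another regimen, so no figure can be put on it. Three things narrow it. The synopsis fixes the doses. The exclusion criteria remove patients whose normal-tissue constraints cannot be met, or in whom comorbidity or prior radiotherapy limits treatment per protocol. Section 16.3 says "Summary compliance measures use the worst observation". None of them says that a patient switched under Section 10.1 is a non-success.

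**The case against.** The strongest reply is that the Protocol already points to one reading. The synopsis labels its endpoint as primary, the aim and the opening of Section 16.1 concern radiotherapy only, and the only measurable threshold in either wording is 90% of the radiation dose. Systemic therapy is an eligibility condition and background care, so the mention of combined treatment may simply describe the setting. The sentence describing the test speaks of feasible cases and does not name the composite. And if systemic completion cannot be scored, an analyst would most likely fall back on the labelled endpoint.

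Much of this supports the choice of fix: the radiotherapy definition is probably what was meant. It does not remove the conflict. The hypothesis sentence comes directly before the test and is the only definition of a feasible case in that section. Read literally, it counts patients who stop systemic therapy as failures. A statistical analysis plan could resolve this only by overriding one of two statements in the Protocol.

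The reply on size stands in part. The systemic completion rates are assumed, and the effect depends on them. If the window is only the radiotherapy course, completion could be high: at an assumed, independent 98% the composite is 0.90 × 0.98 = 88.2% and the rejection probability is 5.6%, against 2.8%. The size of the effect is therefore undetermined, because the window and the criterion are missing.

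It is also fair that the dose gap is a lesser and separate question. The main point stands without it.

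**Conclusion.** The concern holds. The Protocol states two different primary endpoints, and the one in the Section 16.1 hypothesis has a component that the document gives no means of scoring. The sample size is sound under either (23.7, rounded to 24). What changes is the proportion tested. The constructed 24-patient example moves from p = 0.79 to p = 0.014. Under assumed independent systemic completion of 90, 80 or 70%, the rejection probability is 30, 70 or 93%, against 2.8% under the synopsis definition. These figures rest on 90% radiotherapy completion and on systemic rates that the Protocol does not give. They show that the wording can decide the result, and they do not predict what it will be.

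This must be settled before analysis, because it governs the only planned test. The dose gap is real, smaller and not quantifiable from the Protocol.

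**What to change.** - In Section 16.1, delete the words that bring systemic therapy into the hypothesis, and use the synopsis radiotherapy-completion definition throughout.
- Define success as delivery of at least 90% of the Section 10.4 dose to both PTV1 and PTV2.
- State that patients treated on another regimen stay in the denominator and do not count as successes for the study regimen. Also report them as a separate group.
- Report interruptions and changes of systemic therapy descriptively.

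The cost is Protocol wording only. Volumes, fractions and applied doses are already recorded under Section 11.3, current systemic treatment is reviewed at baseline, at the end of radiotherapy and at each follow-up visit, and the sample size does not change. The downside is a possibly lower feasibility figure, since patients on substitute regimens would no longer count as successes.

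### The primary test uses 90% as its null value, so with 24 evaluable patients it can only show feasibility below 90% and can never support the stated hypothesis of at least 90%.

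*Protocol*

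**What the plan says.** The Synopsis gives the primary endpoint as "Proportion of study participants that complete radiotherapy with" at least 90% of the prescribed dose.

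Section 16.1 builds the test on it:

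- Hypothesis: "The hypothesis is that at least 90% of the recruited patients complete combined systemic and local treatment", with at least 90% of the scheduled radiation dose given.
- Test: "We use a two-sided one-sample proportion score test to compare the proportion of feasible cases to a reference value of 90"%.
- Level: "We want to detect any difference with statistical significance of 5"%.
- Power: "power of 80% for not overlooking a true proportion non-feasible of 70"%.
- Size: "The necessary sample size is estimated to 24 cases". With 30% drop-out this becomes 34 patients, who "must be included in the study to reach significance".
- Drop-out: "Drop-out may happen either due to exclusion, or because patients withdraw their consent for participation".

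Neither section 16.1 nor section 16.3 (Analysis) gives a rule for concluding that the treatment is feasible. There is no minimum number of completers, no confidence limit to be exceeded, and no statement that a non-significant result counts as success.

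**The concern.** A significance test can give evidence only against its null value. Here the null value is also the success threshold, and the power is calculated at a lower rate. The test is therefore built to detect that feasibility is worse than 90%, while the text presents the trial as testing whether it is at least 90% and speaks of including enough patients for significance.

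Two things are at stake. If the trial succeeds clinically, the planned analysis has no way of saying so. If the result is not significant, readers may take that as confirmation, although it would also be likely at mediocre completion rates. Fewer evaluable patients would make a non-significant result more likely still, so poor retention would favour an apparent success. Feasibility is the primary endpoint, and section 4 says that a randomised phase II/III study may be suggested on the basis of these results.

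**Working it through.** **Inputs (section 16.1).** Null p0 = 0.90; two-sided level 5%; power 80%; alternative p1 = 0.70; 24 evaluable; 30% drop-out; 34 included.

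**1. The plan's own sample size.**

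n = [(1.96·√(0.9·0.1) + 0.8416·√(0.7·0.3)) / 0.2]² = 23.70, so 24.

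This agrees with the protocol. By the same approximation, power at n = 24 is 80.4%. Reading the alternative literally as 70% non-feasible (30% feasible) would give n = 2.6, so the protocol must mean 70% feasible. For drop-out, 24/0.7 = 34.3, stated as 34.

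**2. Which results are significant.** The score statistic is z = (x/n − 0.9)/√(0.09/n).

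| Result | z | two-sided p |
|---|---|---|
| 24/24 | 1.633 | 0.102 |
| 19/24 | −1.769 | 0.077 |
| 18/24 | −2.449 | 0.014 |
| 34/34 | 1.944 | 0.052 |
| 28/34 | −1.486 | 0.137 |
| 27/34 | −2.058 | 0.040 |

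At n = 24 the upper rejection region is empty, so the probability of a significant result above 90% is 0 whatever the true rate. The exact 95% interval for 24/24 is 85.8% to 100%, which still includes 90%. If all 34 were analysed, 34/34 would just miss by the named test, although one exact test (minimum likelihood) gives p = 0.045. The smallest n at which a perfect result is significant by the score test is 35 (z = 1.972).

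**3. What non-significance would mean.** The test does not reject when x ≥ 19 of 24. The binomial probability of that is:

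- 0.656 at a true rate of 80%
- 0.422 at 75%
- 0.229 at 70%

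The last figure puts exact power at 70% at 1 − 0.229 = 77.1%, slightly below the formula value. A result of 19/24 (79%) is not significant, and its exact 95% interval is 57.8% to 92.9%.

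**4. The same planning values with roles swapped.** Null ≤ 70%, design value 90%, exact binomial.

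| Evaluable | One-sided level | Success if | Size at 70% | Power at 90% |
|---|---|---|---|---|
| 23 | 5% | ≥ 21 | 1.6% | 59% |
| 24 | 5% | ≥ 21 | 4.2% | 79% |
| 25 | 5% | ≥ 22 | 3.3% | 76% |
| 24 | 2.5% | ≥ 22 | 1.2% | 56% |
| 31 | 2.5% | ≥ 27 | 2.4% | 81% |

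The one-sided 95% exact lower limit is 70.8% for 21/24 and 65.8% for 20/24, so 21 is the smallest count that excludes 70%. Under this rule success is declared with probability 26%, 12% and 4% at true rates of 80%, 75% and 70%.

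**The case against.** The best defence is that section 16.1 describes a screen: assume 90%, look for evidence against it, and have 80% power not to miss 70%. On that reading the test fits its purpose, the mention of significance is loose wording for keeping the planned power, and a single-arm feasibility study makes no confirmatory claim. How the conclusion is worded could be left to an analysis plan.

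The test can indeed screen out poor feasibility. But no rule that non-rejection means feasible is written in section 16.1 or 16.3. Such a rule would pass 19/24 and would not show 90% or more. The hypothesis, test and null value are fixed in the protocol, so an analysis plan that followed them would inherit the problem.

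Some narrower objections are fair:

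- Swapping the roles shows a rate above 70%, not at least 90%. It replaces the stated hypothesis with a weaker one, and this must be said openly.
- One-sided 5% is a looser error level than the 2.5% per side of the present test.
- The 23% non-rejection at a true 70% is close to the 20% type II error the sponsor accepted. The weakness shows mainly at 75% and 80%.
- Whether 19/24 excludes a true rate of 60% depends on the level. The two-sided 95% interval does not exclude it, but the one-sided 95% lower limit (61.1%) does.
- At one-sided 2.5%, the 81% power at 31 evaluable is a local peak. It falls to 79%, 77%, 75% and 73% at 32 to 35, and is 85% at 36.

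None of these restores the test's ability to support the stated hypothesis.

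**Conclusion.** The point holds. Under the named score test at two-sided 5% with 24 evaluable patients, no possible data set supports the hypothesis of at least 90%. The only significant finding available is 18/24 or fewer, or 27/34 or fewer if all included patients are analysed. At 34, a perfect result is borderline and its significance depends on the choice of test.

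The fault lies in the direction of the hypothesis, not in the sample size arithmetic. The conclusion assumes that the alternative means 70% feasible, the only reading that reproduces 24. The probabilities assume independent patients with a common completion rate.

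**What to change.** Amend section 16.1 in one of two ways.

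**(a) Swap the planning values.** Null: feasible proportion at most 70%. Design value: 90%. Declare success if the one-sided 95% exact lower limit exceeds 70%, which with 24 evaluable means at least 21/24. State that this shows feasibility above 70%. No extra patients are needed if one-sided 5% is accepted, but power is 79% and depends on the exact number evaluable, so the rule should be given as a lower limit rather than a fixed count. Keeping one-sided 2.5% with 80% power needs 31 evaluable (31/0.7 = 44.3, so 45 included). To hold 80% if slightly more are evaluable, plan for 36 (36/0.7 = 51.4, so 52 included).

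Option (a) also needs a stated denominator. The step from 24 to 34 implies that drop-outs are excluded, whereas the hypothesis refers to recruited patients, which implies that they count as failures. If drop-outs were failures and independent of completion, the planning values would give 0.9 × 0.7 = 63%, already below the 70% null. A rule of at least 30/34 (the one-sided 2.5% cut-off for 34) would then have power of about 0.1% and should not be used.

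**(b) Keep the test and change the claim.** State that it can only show feasibility below 90%, that a non-significant result does not show feasibility, and that the conclusion rests on the observed proportion with its exact 95% confidence interval. This costs only rewording.

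In either case, correct the alternative to 70% feasible and remove the statement that 34 patients are included in order to obtain significance.

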- age ≥ 18 years
- Legal capacity, patient is able to understand the nature, significance and consequences of the trial
- Written informed consent

Exclusion criteria:

- Relevant comorbidity (with limitations to administer radiotherapy according to protocol)
- Prior radiotherapy which results in limitations to administer radiotherapy according to protocol
- No large metal implants in vicinity of lesion
- Department dose constraints for normal tissue can't be met
- Large bony lesions with extensive osseous destruction (e.g. vertebral body)
- Patients symptoms do not correlate with MR findings

7 Risks and toxicities

Patients participating in this study will have standard radiotherapy. Consequently, the participating patients face known risks and toxicities following high dose radiotherapy. Patients participating in this study are offered a higher than normal radiation dose to their dominant lesion, but treatment plans will adhere to department standard dose constraints for all organs at risk in order to avoid excessive risks and toxicities.

8 Registration

The consecutive cohort of HRPC patients will be screened for eligibility according to the inclusion criteria's in this protocol. Estimated median survival for patients to be included should preferably be based on the updated model in (6) (see appendix 1). Before inclusion, patient clinical routine blood lab and radiology results should be reviewed. Available clinical routine diagnostic imaging and lab results may be used to calculate the expected median survival for patients using the model in (6) (see appendix 1). (6)Eligible patients will be informed about the study. After given informed consent, patients may be included in the

study. All patients included in the study receive a patient identification number (PID). The PID is composed of the site number and the running patient number (starting with P01, P02,.. ect.).

Site	SiteID
Naestved, Denmark	C1
Kiel, Germany	C2
Lübeck, Germany	C3

For **pseudonymous** registration and recording of all protocol data, the department of oncology, Naestved, will be make an electronic web interface (Easytrial) available for participating sites.

9 Systemic therapy

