17.2 Study termination in individual patients

Participation in the study and study specific therapy must be stopped at any time during the study in individual patients for any of the following reasons

- withdrawal of informed consent by the patient
- severe toxicity with limitations or unacceptable risks to administer further study therapy
- inter current disease with limitations to administer protocol therapy
- progression of disease

[figure not shown]
18 Ethical and legal aspects

The study will be conducted according to the declaration of Helsinki. Approval by the ethical committees of the participating institution is required prior to initiation of the study. Patients must be fully informed about the study and give informed consent prior to inclusion. National rules for data protection must be obeyed.

The study concept has been evaluated by the expert panel of DEGRO (German Association of Radiation Oncology). Approval by the German Radiation Protection Authority (BfS) is not required. A patient insurance will be taken out before the start of the trial for all patients, if necessary according to national rules. The trial will be registered in a primary study register before the start of the study.

This study receive financial support from EU via the Interreg project.

19 Appendix 1 – Calculation of median survival

20 Appendix 2 – Diagnostic MR Protocol sequences

MR protocols are modified/adapted from (24) and (27) to cover the lesion that explains the dominant symptom.

The MR sequence protocol must contain an anatomical (T2w) axial sequence (reference scan see table below), that can be co-registered to the planning CT, ie. the reference scan must include enough rigid anatomical structures for a co-registration with good accuracy. The remaining MR sequences must cover the dominant lesion with adequate margin (typically 50 mm) that will allow for outline of the lesion in 3D. All MR sequences must be acquired with the same dicom origo, ie neither, the patient nor, the dicom origo may be moved between sequence acquisitions. This will allow all MR images to be co-registered to the planning CT.

Sequence	Directions	Slice mm	TR msec	TE msec	Avg
T2-weighted fast SE	Ax* / Cor / Sag	3/ 5/ 5	2850	80	4
T1-weighted GRE SPIR**	Ax	5	1000	3.7	4
Proton density-weighted fast SE	Ax	5	2850	4.7	4
DW imaging*** with free-breathing SE EPI SPIR*	Ax	5	4687	64	8

Avg = number of sample averages

* Reference scan = T2w axial images

[figure not shown]

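### Section 16.1 sizes the feasibility test as if drop-outs leave the denominator, although an eligible patient who withdraws before 90% of the dose has failed the endpoint

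*Protocol*

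**What the plan says.** The synopsis defines the primary endpoint as "Proportion of study participants that complete radiotherapy with" at least 90% of the prescribed dose. Section 16.1 puts the hypothesis as "at least 90% of the recruited patients complete combined systemic and local treatment with at least 90% of scheduled radiation dose administered". The test is a two-sided one-sample score test against 90%, at 5% significance and 80% power, and needs 24 cases.

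Section 16.1 then continues: "Drop-out may happen either due to exclusion, or because patients withdraw their consent for participation". It adds "For patients with poor prognosis a realistic drop-out rate is estimated to be 30" per cent, and concludes that 34 patients "must be included in the study to reach significance".

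Four other places bear on this:
- Section 17.2: "Participation in the study and study specific therapy must be stopped at any time during the study in individual patients" when one of the listed reasons applies. Withdrawal of consent is the first on the list.
- Section 8 issues the patient identification number (PID) at inclusion.
- Section 10.3 has the protocol MRI done on patients who are already included.
- Section 6 has two exclusion criteria that depend on MR findings or the dose plan: symptoms that do not match the MR findings, and normal-tissue constraints that cannot be met.

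No passage says how a drop-out is scored for the primary endpoint. The rule in 16.3 that compliance summaries take the worst observation does not define a denominator.

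**The concern.** In most trials a drop-out is a patient whose outcome is missing. Here, leaving early can be the outcome. A patient who withdraws consent before 90% of the dose has been given has not completed radiotherapy, and the synopsis endpoint counts exactly that.

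The allowance from 24 to 34 has a purpose only if about 10 included patients are absent from the tested proportion. Section 16.1 therefore points to two denominators for the one primary endpoint: everyone recruited, or those who remain after drop-out. If the second is followed, patients who failed may be left out and feasibility will look better than it was.

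The allowance also merges two kinds of loss: eligible patients who leave, and patients found ineligible after inclusion. The first are failures if they leave before 90% of the dose. Whether the second are failures is a choice that 16.1 does not make.

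**Working it through.** **Inputs (section 16.1).** Reference p0 = 0.90, two-sided alpha 0.05, power 0.80, 30% drop-out. The alternative is printed as 70% non-feasible; I read it as 70% feasible (p1 = 0.70), which reproduces the stated 24.

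**The plan's own figures.**
- n = [(1.96 x sqrt(0.9 x 0.1) + 0.8416 x sqrt(0.7 x 0.3)) / 0.2]^2 = 23.70, so 24.
- 23.70 / 0.7 = 33.9, so 34 (24 / 0.7 = 34.3).

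Both reproduce. The division by 0.7 shows how 34 was obtained. That drop-outs then leave the analysis is an inference from it.

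**When the outcome is known.** Radiotherapy should start within three weeks of inclusion (10.6), and the four fractions should be given within two weeks of the start (10.3). On that schedule the dose outcome is known about 3 + 2 = 5 weeks after inclusion. A patient lost later still has a dose outcome and needs no replacement under the synopsis endpoint. Under the wording of 16.1, which adds systemic treatment, and 16.2, which allows up to six months after the last inclusion, a later loss might matter.

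**Size of the bias.** Let s be the share of the 30% lost before completing and q the share of those who are ineligible. Assume that 90% of all other patients complete. The retained patients show 90%.
- All included: 0.9 x (1 - 0.3s). For s = 0, 0.5 and 1 this is 90%, 76.5% and 63%.
- If every early loss is eligible (q = 0), the overstatement is 0, 13.5 or 27 points.
- Ineligible patients left out: 0.9 x (1 - 0.3s) / (1 - 0.3sq). At s = 0.5, q = 0, 0.5 and 1 give 76.5%, 82.7% and 90%; at s = 1 they give 63%, 74.1% and 90%.

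**Effect on the test.** z = (x/n - 0.9) / sqrt(0.09/n). With 34 analysed, 28/34 = 82.4% gives z = -1.49 (not rejected) and 27/34 = 79.4% gives z = -2.06 (rejected). Six failures are compatible with 90% and seven are not.

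An illustration with invented counts: 34 included; 22 of the 24 retained patients complete; of 10 drop-outs, 5 leave early and 5 leave after completing.

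| Counted | Completers | Rate | z |
|---|---|---|---|
| 24 retained, as sized | 22/24 | 91.7% | +0.27 |
| All included | 27/34 | 79.4% | -2.06 |
| Without 3 of the early 5, if ineligible | 27/31 | 87.1% | -0.54 |
| Without all 5, if ineligible | 27/29 | 93.1% | +0.56 |

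**Exact binomial properties of the same score test** (no upper rejection is possible for n = 24 to 34):

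| n analysed | Reject at or below | Size | Power at true 70% |
|---|---|---|---|
| 24 | 18 | 2.8% | 77% |
| 25 to 33 | 19 to 26 | 2.2% to 5.5% | 81% to 91% |
| 34 | 27 | 4.8% | 92% |

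**The case against.** The best defence is that both stated denominators, recruited patients and study participants, agree and, read literally, keep drop-outs in. A recruitment allowance is not an analysis rule, and the analysis set is often left to a SAP, which is not at hand. It stands that the removal is implied and nowhere stated. It does not follow that nothing needs fixing: if drop-outs are kept in, the stated reason for 34 disappears, and if they are removed, the hypothesis is not about recruited patients. The conflict lies inside one protocol section.

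It is also fair that only consent withdrawals in a window of about five weeks are clearly at issue, and that the protocol does not say how much of the 30% falls there. The bias is therefore a range that starts at nil.

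Two stronger readings are tempting but unsupported:
- A reader might infer that toxicity stops are dropped as exclusions. Section 17.2 does list "severe toxicity with limitations or unacceptable risks to administer further study therapy", but as a reason for ending participation. Section 6 uses exclusion for eligibility criteria, and 16.1 does not link the two.
- A reader might infer that a 30% drop-out already makes the 90% hypothesis unattainable. That requires most drop-outs to be early and every early loss to count as a failure, neither of which is stated. It also judges the result by the observed percentage, whereas the plan uses a score test that tolerates six failures in 34.

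**Conclusion.** The point holds as a conflict within 16.1 that should be resolved. The sizing implies a denominator without drop-outs, while the hypothesis and the synopsis name one with them, and an eligible withdrawal below 90% of the dose is a failure under the synopsis. Following the sizing can only raise the rate with respect to such patients.

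The overstatement lies between nil and 27 percentage points. The upper end assumes that all 30% are eligible early losses and that 90% of the others complete. Nil applies if all losses come after radiotherapy or are genuine ineligibility. With about 10 drop-outs budgeted and the test turning between 6 and 7 failures in 34, the conclusion against 90% can depend on who is removed.

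**What to change.** In 16.1 and the synopsis:
- State that the primary denominator is all included patients, meaning everyone issued a PID.
- Count as not feasible anyone who withdraws or stops before reaching 90% of the prescribed dose. Patients lost after radiotherapy keep their observed dose outcome.
- Report as a sensitivity analysis the rate without patients found ineligible on the post-inclusion MRI or dose plan, with the reasons for loss.
- Reconcile the dose-only endpoint of the synopsis with the combined systemic and local treatment in 16.1.
- Keep 34 but restate its basis: with all 34 analysed, exact power at a true feasible proportion of 70% is 92%, rejecting at 27 or fewer, with size 4.8%. With 25 to 33 analysed, as in the sensitivity analysis, it is 81% to 91%; with 24 it would be 77%.

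The cost is rewording and a restated power calculation, with no extra patients or data. The headline rate may be less favourable, and it mixes post-inclusion ineligibility with treatment delivery, which is why the sensitivity analysis is needed.
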